3.8.2.2. Analysis Windows for B/F/TAF OL Extension Phase

The analysis windows for HIV-1 RNA, CD4 cell count, CD4%, hematology, chemistry, eGFR_{CG}, vital signs, and weight are presented in [Table 3-7](#).

Table 3-7. Analysis Windows for HIV-1 RNA, CD4 Cell Count, CD4%, Hematology^a, Chemistry^b, eGFR_{CG}, Vital Signs, and Weight (B/F/TAF OL Extension Phase)

Visit ID	Nominal Day	Lower Limit	Upper Limit
Baseline			1
Week 4	28	2	56
Week 12	84	57	126
Week 24	168	127	210
Week 36	252	211	294
Week 48	336	295	378
Week 60	420	379	462

a Hematology panel including PT/INR.

b Chemistry profile includes alkaline phosphatase, AST, ALT, GGT, total bilirubin, direct and indirect bilirubin, total protein, albumin, LDH, CPK, bicarbonate, BUN, calcium, chloride, creatinine, glucose, phosphorus, magnesium, potassium, sodium, uric acid, and amylase.

Note: The above analysis windows will also be used for bone biomarker of parathyroid hormone (PTH).

The analysis windows for fasting glucose and lipid panel (total cholesterol, HDL, direct LDL, triglycerides, and total cholesterol to HDL ratio) are presented in [Table 3-8](#).

Table 3-8. Analysis Windows for Fasting Glucose and Lipid Panel (B/F/TAF OL Extension Phase)

Visit ID	Nominal Day	Lower Limit	Upper Limit
Baseline			1
Week 24	168	2	252
Week 48	336	253	420

The analysis windows for SF-36 and HIV-TSQ are presented in [Table 3-9](#).

Table 3-9. Analysis Windows for SF-36 and HIV-TSQ (B/F/TAF OL Extension Phase)

Visit ID	Nominal Day	Lower Limit	Upper Limit
Baseline			1
Week 4	28	2	98
Week 24	168	99	252
Week 48	336	253	420

The analysis windows for safety ECG are presented in [Table 3-10](#).

Table 3-10. Analysis Windows for Safety ECG (B/F/TAF OL Extension Phase)

Visit ID	Nominal Day	Lower Limit	Upper Limit
Baseline			1
Week 48	336	2	504

3.8.3. Selection of Data in the Event of Multiple Records in a Window

Depending on the statistical analysis method, single values may be required for each analysis window. For example, change from baseline by visit usually requires a single value, whereas a time-to-event analysis would not require 1 value per analysis window. When a single value is needed, the following rule(s) will be used.

If multiple nonmissing numeric observations exist in a window, records will be chosen as follows:

- For baseline, the latest available record on or prior to the first dose of E/C/F/TAF or B/F/TAF study drug, as appropriate, will be selected. If there are multiple records with the same time or no time recorded on the same day, average will be used for the baseline value, except for HIV-1 RNA (see below).

- For postbaseline visits:

For CD4 cell count and CD4%, the record(s) collected on the latest day in the window will be selected for analysis.

For other numeric observations (except HIV-1 RNA), the record(s) collected on the day closest to the nominal day for that visit will be selected. If there are 2 records equidistant from the nominal day, the later day will be selected.

For any numeric observations except HIV-1 RNA, if there are multiple records on the selected day, the average will be taken.

- For baseline and postbaseline HIV-1 RNA, the latest (considering both date and time) record(s) in the window will be selected. If both “HIV RNA Taqman 2.0” and “HIV RNA Repeat” (ie, the HIV-1 RNA result obtained from an additional aliquot of the original sample) are available with the same collection time, the results from the “HIV RNA Repeat” will be selected for analysis purposes; otherwise, if there are multiple “HIV RNA Taqman 2.0” records with the same collection time, the geometric mean will be taken for analysis purposes.

If multiple valid nonmissing categorical observations exist in a window, records will be chosen as follows:

- For baseline, the last available record on or prior to the first dose of E/C/F/TAF or B/F/TAF study drug, as appropriate, will be selected. If there are multiple records with the same time or no time recorded on the same day, the value with the lowest severity will be selected (eg, normal will be selected over abnormal for safety ECG findings).
- For postbaseline visits, the most conservative value within the window will be selected for categorical observations other than patient reported outcomes (eg, abnormal will be selected over normal for safety ECG findings).
- For patient-reported outcomes collected at postbaseline visits, the record closest to the nominal day for that visit will be selected. If there are 2 records equidistant from the nominal day, the later will be selected.

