8.1.3. Secondary Endpoints

- Incidence of treatment-emergent grade 3 or higher adverse events up to Week 96 in subjects receiving E/C/F/TAF
- Proportion of subjects receiving E/C/F/TAF with HIV-1 RNA < 50 copies/mL at Weeks 24, 48, and 96 as defined by the FDA snapshot algorithm
- The pharmacokinetics parameters of EVG, COBI, FTC, TAF and TFV, **CCI** [REDACTED]

Similar safety and tolerability measures will be used to characterize the safety and tolerability of B/F/TAF in HIV-1 infected patients with ESRD on chronic HD.

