3. GENERAL CONSIDERATIONS FOR DATA ANALYSES

The final analysis will include all data collected from the E/C/F/TAF and the B/F/TAF OL extension phases of the study. Separate tables and figures will be created for each phase unless otherwise specified. Data collected from both phases will be included in data listings. Data included in each phase are defined as follows:

E/C/F/TAF Phase Data

- For subjects who are never treated in the B/F/TAF OL extension phase of the study, all available data are considered as the E/C/F/TAF phase data.
- For subjects treated in the B/F/TAF OL extension phase of the study, E/C/F/TAF phase data are defined as data collected **up to** the B/F/TAF OL extension phase first dose date except for data on adverse events (AEs), concomitant medications, pregnancy, and death. For AEs, concomitant medications, pregnancy, and death, only data collected **prior to** the B/F/TAF OL extension phase first dose date are included.

B/F/TAF OL Extension Phase Data

- B/F/TAF OL extension phase data are only available from subjects who enter the B/F/TAF OL extension phase of the study. B/F/TAF OL extension phase data are defined as data collected **after** the B/F/TAF OL extension phase first dose date except for data on AEs, concomitant medications, pregnancy, and death. For AEs, concomitant medications, pregnancy, and death, data collected **on or after** the extension phase first dose date are included.

Analysis results will be presented using descriptive statistics. For categorical variables, the number and percentage of subjects in each category will be presented; for continuous variables, the number of subjects (n), mean, standard deviation (SD) or standard error (SE), median, first quartile (Q1), third quartile (Q3), minimum, and maximum will be presented.

By-subject listings will be presented for all subjects in the All Enrolled Subjects Analysis Set unless otherwise specified, and sorted by subject ID number, visit date, and time (if applicable). Data collected on log forms, such as AEs, will be presented in chronological order within a subject.

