7.1. Efficacy Endpoints as Secondary Study Endpoints

Secondary efficacy endpoints for the final analysis include the following:

- The proportion of subjects with HIV-1 RNA < 50 copies/mL at Week 96 as defined by the US FDA-defined snapshot algorithm
- The proportion of subjects with HIV-1 RNA < 50 copies/mL by visit
- The change from baseline in CD4 cell count and CD4% by visit

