7.2. Analysis of Efficacy Endpoints

7.2.1. Analysis of the Proportion of Subjects with HIV-1 RNA < 50 copies/mL at Week 96 as Determined by US FDA-defined Snapshot Algorithm

US FDA-Defined Snapshot Algorithm

The analysis window at Week 96 is defined as from Study Day 631 to Study Day 714, inclusive. All HIV-1 RNA data collected on-treatment (ie, data collected up to 1 day after the last dose date of E/C/F/TAF study drug) will be used in the US FDA-defined snapshot algorithm. Virologic outcome for Week 96 will be defined using the following categories:

- **HIV-1 RNA < 50 copies/mL:** this includes subjects who have the last available on-treatment HIV-1 RNA < 50 copies/mL in the analysis window
- HIV-1 RNA \geq 50 copies/mL: this includes subjects
 - 1) Who have the last available on-treatment HIV-1 RNA \geq 50 copies/mL in the analysis window , or
 - 2) Who do not have on-treatment HIV-1 RNA data in the analysis window and
 - a) Who discontinue study drug prior to or in the analysis window due to lack of efficacy, or
 - b) Who discontinue study drug prior to or in the analysis window due to AE or death and have the last available on-treatment HIV-1 RNA \geq 50 copies/mL, or
 - c) Who discontinue study drug prior to or in the analysis window due to reasons other than AE, death, or lack of efficacy and have the last available on-treatment HIV-1 RNA \geq 50 copies/mL

- **No Virologic Data in Window:** this includes subjects who do not have on-treatment HIV-1 RNA data in the analysis window because of the following:
 - 3) Discontinuation of study drug prior to or in the analysis window due to AE or death and the last available on-treatment HIV-1 RNA < 50 copies/mL, or
 - 4) Discontinuation of study drug prior to or in the analysis window due to reasons other than AE, death, or lack of efficacy and the last available on-treatment HIV-1 RNA is < 50 copies/mL, or
 - 5) Missing data during the window but on study drug

The flowchart of the snapshot algorithm is provided in [Appendix 3](#).

The number and percentage of subjects with HIV-1 RNA < 50 copies/mL, HIV-1 RNA ≥ 50 copies/mL, and reasons for no virologic data at Week 96 will be summarized using the E/C/F/TAF FAS. The 95% confidence intervals (CIs) for percentages of subjects with HIV-1 RNA < 50 copies/mL and HIV-1 RNA ≥ 50 copies/mL will be constructed using the Exact method (see [Appendix Table 1](#)[Appendix Table 2](#)).

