7.2.2. Analysis of Other Efficacy Endpoints

7.2.2.1. By-Visit Analysis of the Proportion of Subjects with HIV-1 RNA < 50 copies/mL by Missing Failure and Missing Excluded Approaches

The proportion of subjects with HIV-1 RNA < 50 copies/mL will be summarized using the following 2 methods for imputing missing HIV-1 RNA values:

- Missing Failure (M F)

In this approach, all missing data will be treated as HIV-1 RNA ≥ 50 copies/mL. The denominator for percentages is the number of subjects in the E/C/F/TAF FAS.

- Missing Excluded (M E)

In this approach, all missing data will be excluded in the computation of the percentages (ie, missing data points will be excluded from both the numerator and denominator in the computation). The denominator for percentages at a visit is the number of subjects in the FAS with nonmissing HIV-1 RNA value at that visit.

For both M-F and M-E analyses, the number and percentage of subjects with HIV-1 RNA in the following categories will be summarized (see [Appendix Table 3](#)):

- < 50 copies/mL
 - < 20 copies/mL
 - < 20 Not Detectable
 - < 20 Detectable
- 20 to < 50 copies/mL
- \geq 50 copies/mL

The 95% CIs of the proportion of subjects with HIV-1 RNA < 50 copies/mL will be provided using the Exact method.

Separate summaries will be provided for the E/C/F/TAF FAS and the B/F/TAF FAS.

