7.2.2.2. Analysis of CD4 Cell Count and CD4 %

Values and changes from baseline in CD4 cell count and CD4% will be summarized at each postbaseline visit using descriptive statistics based on observed on-treatment values. On-treatment values include data collected after the first dose date up to the applicable last dose date + 1 day for subjects who permanently discontinued the applicable study drug.

In addition, values and changes from baseline in CD4 cell counts with missing values imputed using the last observation carried forward (LOCF) method will be summarized at each postbaseline visit. The algorithm for LOCF is as follows:

- If a value is missing in an analysis visit window, the missing value will be replaced with the last on-treatment value (ie, up to 1 day after the last dose date of applicable study drug) observed before the analysis visit window that has the missing value.
- Baseline values will not be used for imputation; subjects who had no postbaseline CD4 assessment will be excluded from the postbaseline summaries.

The mean and 95% CI and median (Q1, Q3) of values and change from baseline in CD4 cell count over time will be plotted using observed data.

Separate summaries will be provided for the E/C/F/TAF FAS and the B/F/TAF FAS.

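### In the by-visit HIV-1 RNA summaries (M=F and M=E), the off-drug 30-Day Follow-Up sample can replace a completer's on-drug Week 96 value, and the Week 48 OL value if B/F/TAF stops at about that visit

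*SAP*

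**What the plan says.** **Selection rule.** SAP 3.8.3: "For baseline and postbaseline HIV-1 RNA, the latest (considering both date and time) record(s) in the window will be selected". Most other numeric measures take the record closest to the nominal day. CD4 also takes the latest day in the window.

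**By-visit summaries.** SAP 7.2.2.1: "The proportion of subjects with HIV-1 RNA < 50 copies/mL will be summarized using the following 2 methods for imputing missing HIV-1 RNA values". Neither method is restricted to samples taken on study drug. The M=E denominator is everyone with a nonmissing value at the visit.

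**Neighbouring analyses.** The snapshot (SAP 7.2.1) uses "All HIV-1 RNA data collected on-treatment (ie, data collected up to 1 day after the last dose date of E/C/F/TAF study drug"). For CD4 (SAP 7.2.2.2): "On-treatment values include data collected after the first dose date up to the applicable last dose date + 1 day".

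**Phase data.** Under SAP 3, for subjects never treated with B/F/TAF, "all available data are considered as the E/C/F/TAF phase data". B/F/TAF phase data have a start point but no cut-off after the last dose. For rollover subjects, E/C/F/TAF data end at the first B/F/TAF dose.

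**Follow-up sample.** Protocol 6.5.1 includes plasma HIV-1 RNA at the 30-Day Follow-Up, with a tolerance of 6 days either way. SAP 1.2 has subjects who do not plan to enter the extension stop drug after Week 96 and attend this visit.

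**Status.** SAP 7.1 lists "The proportion of subjects with HIV-1 RNA < 50 copies/mL by visit" as a secondary efficacy endpoint. Protocol 8.1.3 has only the snapshot version: "Proportion of subjects receiving E/C/F/TAF with HIV-1 RNA < 50 copies/mL at Weeks 24, 48, and 96 as defined by the FDA snapshot algorithm".

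**The concern.** A value reported as Week 96 should describe viral load on E/C/F/TAF at about that visit. Under the rules as written, a completer who stops on schedule has two samples in the Week 96 window: one at the visit, on drug, and one about 30 days after stopping. The rule takes the second. CD4 from the same follow-up visit is excluded by its on-treatment limit, while HIV-1 RNA is kept.

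A completer could then be counted below 50 copies/mL at Week 96 by snapshot and at or above 50 by M=F, or the reverse, with nothing in the table to explain it. The M=F and M=E tables are also the only virologic response summary planned for B/F/TAF, so the extension has no snapshot to set beside them.

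**Working it through.** **Inputs**

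| Item | Value | Source |
|---|---|---|
| Week 96 window | Days 631-714, nominal 672 | SAP Table 3-1 and 7.2.1 |
| Week 48 OL window | B/F/TAF Days 295-378, nominal 336 | SAP Table 3-7 |
| Visit tolerance | 6 days either way (Week 96 default; OL visits after Week 4 OL) | Protocol 6.3, 6.4.3 |
| Follow-up timing | 30 days, 6 days either way | Protocol 6.5.1 |
| E/C/F/TAF FAS | 55 | SAP Appendix Table 1 |

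**Step 1: reproduce the windows.** The limits are midpoints between nominal days.
- Week 96: (588 + 672)/2 + 1 = 631; (672 + 756)/2 = 714.
- Week 48 OL: (252 + 336)/2 + 1 = 295; (336 + 420)/2 = 378.

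Both agree with the SAP.

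**Step 2: place the follow-up sample.** Assume drug stops on the visit day, so follow-up comes 24 to 36 days later. For the extension, assume the first B/F/TAF dose is on the day from which OL visits are scheduled.
- Week 96: earliest 672 - 6 + 24 = 690; latest 672 + 6 + 36 = 714.
- Week 48 OL: earliest 336 - 6 + 24 = 354; latest 336 + 6 + 36 = 378.

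There are 13 visit days and 13 follow-up offsets, so 169 timing pairs. All 169 fall inside the window in each phase. SAP 3.8.1 adds 1 to the date difference, so an on-time visit is Study Day 673 (or 337). The ranges become 691-715 and 355-379, and 168 of 169 pairs fall inside. In every pair the follow-up is later than the visit sample. These are calendar combinations, not a proportion of subjects.

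**Step 3: where the overlap ends.** With follow-up exactly 30 days after the visit, the sample stays in the window up to a visit on Day 714 - 30 = 684, or a last dose on Day 378 - 30 = 348 in the extension. After that it falls in the next window and no longer replaces the visit value. This matters because the sponsor can widen the Week 96 visit window to 6 weeks either way.

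**Step 4: later stops.** A subject who continues and then stops at a scheduled Week 108 visit without rolling over has the same overlap: 756 + 18 = 774 to 756 + 42 = 798, inside 715-798.

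**Step 5: look for an exclusion.** SAP 3, 3.8.3 and 7.2.2.1 contain none. SAP 3.8.1 does exclude the 30-day follow-up date when a missing last dose date is imputed, but that exclusion does not extend to record selection.

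**Step 6: size per subject.** One reclassified subject moves Week 96 M=F by 1/55 = 1.8 points. As an illustration only, 45/55 = 81.8% would become 44/55 = 80.0%. In the extension, at least 7 of the 55 had stopped drug early by Week 48 (Protocol 1.2.5) and could not roll over (Protocol 6.5.2), so N is at most 48. If the B/F/TAF FAS is the denominator, one subject is at least 1/48 = 2.1 points.

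**The case against.** The rule is explicit and deterministic, and leaving out an on-treatment limit could be deliberate. Protocol 6.3 keeps evaluating subjects whether or not they still take study drug. Protocol 1.3.3.4 describes a sister study whose M=F and M=E sets include subjects who had stopped study drug but had data at the analysis time point. This part stands: a reader might infer that all off-drug values should be removed from M=F and M=E, and the documents do not support that. For example, take a subject with an on-drug value on Day 635 who stops on Day 640 and attends the scheduled Week 96 visit off drug on Day 672. A blanket on-treatment preference would discard the scheduled value and move these tables towards the snapshot they complement. The convention does not reach the present case, however. It concerns discontinuers with data at the time point, and it gives no reason to replace a completer's valid visit value with a post-treatment sample.

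It is also fair that the Week 48 OL case is conditional. Treatment is for at least 48 weeks, dispensing is marked at Week 48 OL in Protocol Appendix 3, and there is a Week 60 OL window. Nothing shows that anyone stops at Week 48 OL.

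A reader might also take the interim Week 48 results in Protocol 1.2.5 (M=F 83.6%, snapshot 81.8%) as evidence that follow-up samples have already displaced on-drug values. They do not show that. Completers have no 30-Day Follow-Up at Week 48; an early discontinuer still attending visits, or an early-discontinuation draw, could explain the gap; and the analysis plan in force then is not among the documents.

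Finally, the stakes are modest. No formal testing is planned (SAP 3.5), and the protocol's virologic endpoint is the snapshot.

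**Conclusion.** The point holds within narrow bounds and is worth fixing. For a subject who stops E/C/F/TAF at an on-schedule Week 96 visit without rolling over and attends follow-up, selection of the off-drug sample is the ordinary result of the written rules. For B/F/TAF the same follows only if dosing stops at about Week 48 OL. Rollover subjects are unaffected in the E/C/F/TAF phase.

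The result changes only where a subject's category differs between the two samples. The documents give neither the number of subjects who stop at Week 96 without rolling over nor the antiretrovirals they take afterwards. The number affected and the direction of bias are therefore unknown. It would go too far to conclude that the trial's Week 96 response rate is wrong: the snapshot, the primary endpoint and the CD4 analyses do not use these records.

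**What to change.** In SAP 3.8.3, with a cross-reference from 7.2.2.1, state that for M=F and M=E a 30-Day Follow-Up HIV-1 RNA record is not selected when the window also holds an on-treatment record, meaning one dated up to the applicable last dose date plus 1 day. In that case select the latest other record in the window. Keep follow-up values in the listings. Leave the handling of scheduled off-drug visits by early discontinuers unchanged.

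The cost is one selection rule, using the visit label and an on-treatment flag that the snapshot and CD4 analyses already need. The SAP is signed and the Week 24, 48 and 96 analyses have been run, so this is a late change. SAP 1 already provides for documenting such changes in the final study report. Footnote any difference from the M=F and M=E results already reported.

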4. SUBJECT DISPOSITION

4.1. Subject Enrollment and Disposition

4.1.1. Subject Enrollment

The number and percentage of subjects enrolled for each country and investigator will be summarized using the E/C/F/TAF Safety Analysis Set and the B/F/TAF Safety Analysis Set. The denominator for these summaries will be the number of subjects in the respective Safety Analysis Set.

A listing of subject enrollment including date of informed consent signed and met all eligibility criteria will be provided (see [Appendix Listing 1](#)).

4.1.2. Subject Disposition

A summary of subject disposition will be provided (see [Appendix Table 1](#)). This summary will include the number of subjects screened, screen failure subjects who were not enrolled, subjects who met all eligibility criteria and were not enrolled, subjects enrolled, subjects enrolled but not treated, subjects in the E/C/F/TAF Safety Analysis Set, subjects in the B/F/TAF Safety Analysis Set, subjects in the E/C/F/TAF FAS, and subjects in the B/F/TAF FAS.

In addition, the number and percentage of subjects in the following categories will be summarized:

- Completed E/C/F/TAF study treatment
- Prematurely discontinued E/C/F/TAF study treatment (with summary of reasons for discontinuing study drug)
- Enrolled in the B/F/TAF OL extension phase of the study
- Completed B/F/TAF OL study treatment
- Prematurely discontinued B/F/TAF OL study treatment (with summary of reasons for discontinuing study drug)
- Completed the study
- Prematurely discontinued from the study (with summary of reasons for discontinuing study)

The denominator for the percentages of subjects in each category, except for the categories of “completed B/F/TAF OL study treatment” and “prematurely discontinued B/F/TAF OL study treatment”, will be the number of subjects in the E/C/F/TAF Safety Analysis Set. The denominator for the percentage of subjects in the categories of “completed B/F/TAF OL study treatment” and “prematurely discontinued B/F/TAF OL study treatment” will be the number of subjects in the B/F/TAF Safety Analysis Set.

No inferential statistics will be generated. Data listings of reasons for premature study drug discontinuation and premature study discontinuation will be provided.

4.2. Extent of Study Drug Exposure and Adherence

4.2.1. Duration of Exposure to E/C/F/TAF Study Drug

Duration of exposure to E/C/F/TAF study drug will be defined as (the last E/C/F/TAF dose date Study Day 1 + 1), regardless of temporary interruptions in study drug administration, and will be expressed in weeks using up to 1 decimal place (eg, 4.5 weeks).

Duration of exposure to E/C/F/TAF study drug will be summarized using descriptive statistics (n, mean, SD, median, Q1, Q3, minimum, and maximum) and as the number and percentage of subjects exposed for specified periods, ie, \geq 2 weeks (14 days), \geq 4 weeks (28 days), \geq 8 weeks (56 days), \geq 12 weeks (84 days), \geq 24 weeks (168 days), \geq 36 weeks (252 days), \geq 48 weeks (336 days), \geq 60 weeks (420 days), \geq 72 weeks (504 days), \geq 84 weeks (588 days), \geq 96 weeks (672 days), \geq 108 weeks (756 days), etc.

Summaries will be provided for subjects in the E/C/F/TAF Safety Analysis Set. No inferential statistics will be provided.

Time to premature discontinuation of E/C/F/TAF study drug will be analyzed using the Kaplan-Meier (KM) method based on the E/C/F/TAF Safety Analysis Set. Subjects who completed E/C/F/TAF study treatment will be censored on the last E/C/F/TAF dose date. A plot of KM estimates for time to premature discontinuation of E/C/F/TAF study drug will be generated.

